2.2 Stage 2: Application of the sustainable-psycho-nutritional intervention program

2.2.1 Participants

Once the intervention program has been designed, it will be applied to a sample of Mexican young adults from the south of Jalisco, randomly divided into two groups: an experimental group (n=50) and a control group (n=50). This is based on recommendations for group designs in behavior modification programs (38). The sample size is according to the minimum suggested for nutritional interventions (39,40), and taking into account the possible desertion of the participants during the intervention, which can amount to more than 50% of the initial sample (41). We will include a population between 18 and 35 years old, with Body Mass Index (BMI) values from 18.5 to 40, with or without risk factors for the development of chronic diseases, but without diagnosis with previous pharmacological treatment. The inclusion, exclusion, and elimination criteria are detailed in Supplementary Material 2 in Table SM2.1. Also, for being included in the study cut-off points to identify inadequate consumption and physical activity were established (Table SM2.2). The population will be invited to participate through social networks and posters at strategic points, such as Universities, gyms, and the downtown city. Young adults were selected as the population for this study since they are already considered adults who make autonomous food decisions, but at the same time, their young age makes them susceptible to behavioral modification. In addition, they represent parents or future parents, as well as the active population of Mexico, so providing nutritional-sustainable education to these people could generate long-term benefits for their health and that of their families (21,42,43).

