2.2.2 Procedure

Participants will be evaluated following the nutritional care process model (44). The first evaluation will be performed at the beginning of the intervention at baseline, and according to individual requirements, the behavioral objectives will be individually adapted and will be addressed for 7 weeks, considering 2 objectives per week, thus providing 2 weekly educational workshops. Also, personalized food plans will be prescribed, according to the linear programming optimization (29,30) performed at MATLAB®.

After 7 weeks of educational and nutritional intervention, at week 8, the experimental population will be divided into two sub-groups, where one group will stop being intervened completely (n = 25), and another will continue to receive messages through the mobile application (n = 25) for 8 weeks. Finally, at week 15, a final evaluation will be carried out. The study design is shown in Figure 2. Participants will be evaluated in the regard of Anthropometric, Biochemical, Clinical, Dietetics, Environmental, Socioeconomic level and cultural aspects,

Nutritional-sustainable knowledge, Behavioral aspects, and Physical activity (ABCD-ESNBP). These aspects will be evaluated according to the nutritional care process model, thus identifying the problem of the population, establishing the etiology, and stating the signs and symptoms (44).

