2.2.3 Sustainable-psycho-nutritional indicators

The ABCD-ESNBP indicators will be included in a complete clinical history that will be uploaded to the mobile application (Supplementary Material 3) and will be evaluated as follows: A) Anthropometric: height with a Smartmet® stadiometer, weight, and body composition (percentage of body fat, muscle mass, visceral fat) with an Omron® bioimpedance scale (HBF-511T-E/HBF-511B-E), $BMI = \text{weight}/\text{height}^2$, waist and hip circumference using a Lufkin® metal tape measure. The assessment will be performed following the validated techniques of Suverza and Haua (45).

B) Biochemical: glucose and lipid profiles (TC, LDL-C, HDL-C, and TG) will be determined through blood samples that will be taken from the antecubital vein of each participant, following the protocol from the Mexican Health Secretary (46,47). Samples will be taken by specialists, after an overnight fast of 8 to 12 hours and will be centrifuged at 3500 rpm for 15 min to separate the serum. Samples will be aliquoted and stored at -20°C until the day of testing. Tourniquets, alcohol swabs, 10 mL syringes, and blood collection tubes will be required. Gut microbiota will also be analyzed, for which fecal samples will be collected in a sterile stool container using a sterile kit including gloves and a spatula that will be delivered to the participants. Once collected, the samples will be divided into aliquots and will be stored at -80 °C, following a method used for the Mexican population (4,48).

C) Clinical: a clinical history will be carried out, covering pathologies suffering, pathological family history, medicaments, and supplement use (Supplementary Material 3). Clinical signs of insulin resistance (acanthosis nigricans) will be evaluated by physical exploration, searching for hyperpigmentation and thickening of the skin with velvety, in visible flex areas (axilla, anterior ulnar area, and posterior and lateral region of the neck) (49). Signs of nutrient deficiencies or excess will also be evaluated in relation to hair, nails, mouth, tongue, edema, and mucous membranes appearance (45). Likewise, blood pressure will be evaluated with a Medstar® sphygmomanometer and following the Mexican normativity (50).

[figure not shown]

Figure 2. Study design for stage 2. Own elaboration.

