Note: this table will be updated according to the linear optimization programming.

Supplementary Material 2. Inclusion, exclusion, and elimination criteria

Table SM2.1. Inclusion, exclusion, and elimination criteria

Study Criteria		
Inclusion	Exclusion	Elimination
Being between 18 and 35 years old	Not signing the informed consent	Not completing the questionnaires
Being Mexican	Not accepting to donate blood and/or stool samples	Do not allow the extraction of blood and / or delivery of stool sample
Reside in the South of Jalisco for at least 1 year	Not being able to stand up to take anthropometric data	Failure to complete the 7-week intervention or 7-week follow-up
Levels of physical activity below what is recommended and what is established as a criterion for inclusion in the study (Table SM2)	Perform levels of physical activity above the minimum established as criteria for inclusion in the study (Table SM2)	
Consuming amounts of food below or above that established as criteria for inclusion in the study or in a lesser or greater frequency than recommended, according to the type of food (Table SM2)	Consume adequate levels of the foods to be promoted in the intervention program (Table SM2)	
Have a Smartphone	Being pregnant or lactating	
Not having consumed antibiotics at least 3 months before the intervention	Suffer from a chronic disease such as type 2 diabetes mellitus, arterial hypertension, dyslipidemia, under medication	
Have a BMI between 18.5 and 40	Suffering from an autoimmune disease such as type 1 diabetes, hypo or hyperthyroidism	
Not having a medical diagnosis of chronic disease under pharmacological treatment	Having a gastrointestinal disease such as Crohn's disease, ulcerative colitis, etc.	
Not having a medical diagnosis of gastrointestinal disease	Having used antibiotics less than 3 months ago	
	Taking antidepressant medications or corticosteroids	
	Consume probiotics or nutritional supplements, except protein powder	

Table SM2.2 Cut-off points to establish inadequate consumption and physical activity, to be included in the research

Physical activity	Inclusion criteria	
	Light	
	< 3 times per week	< 30 minutes per day
Type of physical activity		
Weekly frequency		
Minutes per day		
Food group	Consumption to be included in the study	Frequency of consumption to be included in the study
Mexican food and dishes	< 100 g p ⁻¹ d ⁻¹	< 7 times a week
Fruits	< 400 g p ⁻¹ d ⁻¹	< 7 times a week
Vegetables	< 400 g p ⁻¹ d ⁻¹	< 7 times a week

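### Elimination in Table SM2.1 is undefined and section 2.3.4 names no analysis set; on the natural reading the randomised comparison becomes a completer comparison that can discard usable data

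*Combined protocol and SAP*

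**What the plan says.** Section 2.2.1 has the sample "randomly divided into two groups: an experimental group (n=50) and a control group (n=50" and refers to Table SM2.1 for the criteria. That table has three columns: inclusion, exclusion and elimination. The elimination column contains three entries:

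- "Not completing the questionnaires"
- "Do not allow the extraction of blood and / or delivery of stool sample"
- "Failure to complete the 7-week intervention or 7-week follow-up"

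The exclusion column already has a sample criterion for entry: "Not accepting to donate blood and/or stool samples".

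No visible text says what happens to the data of someone who is eliminated. Section 2.3.4 lists paired and unpaired tests, correlations and regressions, but no analysis set and no rule for missing data. Section 2.2.1 says that the sample size was chosen "taking into account the possible desertion of the participants during the intervention, which can amount to more than 50% of the initial sample". On assessment, section 2.2.2 describes a baseline evaluation and then says: "Finally, at week 15, a final evaluation will be carried out".

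**The concern.** The non-completion criterion can only act after the random division. The sample criterion probably does too, since refusal at entry is already covered by exclusion. The timing of the questionnaire criterion is not stated. A third column beside inclusion and exclusion, in a plan whose sample size allows for desertion, reads most naturally as removal from the study and its analysis. Nothing in section 2.3.4 would keep these people in.

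Two things would follow. First, the groups compared would be completers rather than the groups as randomised, and the plan would give no reason to assess someone who stops the programme. Second, a participant lacking one item would be lost from outcomes that do not use it. Section 2.2.3 shows that only the microbiota outcome needs stool: "glucose and lipid profiles (TC, LDL-C, HDL-C, and TG) will be determined through blood samples", and the water and carbon footprints are calculated for the diet.

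The between-group result may be biased if completion is related to outcome differently by arm, or if it is related to outcome and retention differs by arm. The visible text does not say what completing the intervention means for a control, so unequal selection is possible. The paired tests gain completer bias if completion is related to change. This comes on top of any regression to the mean, since Tables SM2.1 and SM2.2 select people for inadequate diet and activity.

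**Working it through.** **The plan's own figure.** The 50 per arm cannot be reproduced, because section 2.2.1 gives no significance level, power, effect size or SD. The one usable input is the possible desertion: at 50% loss, 50 × 0.5 = 25 completers per arm remain.

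**Assumed inputs (none from the documents).** No true effect; 25 of 50 complete in each arm; completion is related to outcome in the experimental arm only. Rho is the correlation between the tendency to complete and favourable change, taken as 0.2, 0.3 and 0.5. E is the number per arm who could be assessed but are eliminated. Those lost entirely are assumed to have the lowest tendency to complete.

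**Bias added by the rule.** If a fraction p of the experimental arm is kept, its mean shifts by rho × k(p), where k(p) = φ(z)/p and z is the standard normal cut-off exceeded with probability p.

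- k(0.50) = 0.798 (completers only)
- k(0.60) = 0.644 (E = 5 also kept: 30 of 50)
- k(0.75) = 0.424 (E = 12.5 also kept: 37.5 of 50)

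The rule adds rho × [k(0.50) − k(p)]:

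| E per arm | Factor | rho 0.2 | rho 0.3 | rho 0.5 |
|---|---|---|---|---|
| 0 | 0 | 0 | 0 | 0 |
| 5 | 0.154 | 0.03 SD | 0.05 SD | 0.08 SD |
| 12.5 | 0.374 | 0.07 SD | 0.11 SD | 0.19 SD |

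With equal selection and retention in both arms the bias is 0 at every rho.

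**Type I error of the unpaired test (nominal 5%, 40,000 simulated trials per setting; rho 0.2, 0.3, 0.5).** Completers only: 9%, 13%, 30%. With E = 5 kept: 8%, 12%, 25%. With E = 12.5 kept: 7%, 9%, 16%.

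**Precision (noncentral t, two-sided 5%, 80% power).** The detectable difference is 0.81 SD with 25 per arm, 0.74 SD with 30 and 0.66 SD with 37.5. As a check, the normal approximation for 25 per arm is (1.960 + 0.842) × √(2/25) = 0.79 SD.

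**Stool only.** If 10% or 20% of 50 per arm refuse stool alone (assumed), 5 or 10 per arm are discarded from outcomes that do not need it. The detectable difference then goes from 0.57 SD to 0.60 or 0.63 SD.

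**The case against.** The strongest reply is that removal from the analysis is inferred. No sentence says that eliminated people leave the analysis, and elimination could mean leaving the programme only. That is correct. It leaves an undefined term and no analysis set, so the choice between readings could still be made after the data are seen.

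A second reply is that the rule may reach few assessable people. Section 2.3.3 and the questionnaire in Supplementary Material 6 expect graded adherence among those who stay, so completing need not mean full adherence. Section 2.2.2 does not limit the week-15 evaluation to completers. It also has one week-8 subgroup receive no further intervention, so for that subgroup failing follow-up largely means missing week 15, which leaves no final outcome to discard. The text names only baseline and week-15 evaluations. Figure 2 is not shown, so an end-of-intervention measurement can be neither confirmed nor ruled out. All this stands and points to a small E, possibly near 0.

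Third, most of the inflated type I error above is ordinary attrition: at rho 0.3 and E = 5 it is 13% with the rule and 12% without it. That stands too. The loss of precision from stool refusal is likewise modest.

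A reader might infer that the plan prescribes a biased analysis, that half the sample will be lost, or that every deserter could have been measured. The documents support none of these. Removal is not stated, desertion above 50% is given as a possibility, and people who desert may well be unavailable for assessment.

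**Conclusion.** The point holds as a gap with a likely harmful reading. A rule that acts after randomisation has no stated consequence for the analysis, and nothing in section 2.3.4 protects the groups as randomised or the outcomes already measured. Whether bias arises, in which direction and how large, cannot be known from the documents. In the illustration the rule adds between 0 and 0.19 SD for E from 0 to 12.5 per arm, and it costs up to 0.15 SD in detectable difference (0.81 against 0.66 SD). These figures rest wholly on the assumed rho, E, 50% completion and selection in one arm.

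It should be fixed, before any data are seen. With E unknown and possibly 0, it cannot be called a fatal flaw. The case for acting is that the rule touches every outcome, that people who are not assessed may be unrecoverable, and that the remedy is cheap.

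**What to change.** - Define elimination in Table SM2.1. State there and in section 2.3.4 that, whatever it means for taking part in the programme, it is not a ground for exclusion from analysis.
- Analyse participants in their assigned arm, outcome by outcome, with all available data, so that a missing stool sample affects only the microbiota analysis.
- Invite those who stop the programme and have not withdrawn consent to the week-15 evaluation that is already planned.
- Report losses and reasons by arm.
- Keep completers as a labelled secondary analysis, with completion defined for controls and for the two week-8 subgroups.
- Reconcile the period after the intervention, on which the rule depends: it is 7 weeks in the abstract and Table SM2.1, but section 2.2.2 gives 8 weeks for the app messages.

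The cost is a few sentences and some effort to contact people who stop. The estimated effect may be smaller than among completers. Bias from people with no outcome data remains: in the illustration with E = 12.5 kept, rho × 0.424 gives 0.08, 0.13 and 0.21 SD for rho 0.2, 0.3 and 0.5.
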